## 10.2 STATISTICAL HYPOTHESIS

Treatment with SG will result in a higher ORR than standard-of-chemotherapy regimen (> 15% ORR).

## 10.3 SAMPLE SIZE DETERMINATION

The sample size calculation is determined based on the same calculations for each of the three cohorts separately. In participants with recurrent/metastatic ovarian cancer, endometrial cancer, and cervical cancer, previous studies suggest that response ranges from approximately 10-15% using single agent chemotherapy [25, 26], which is what we aim to improve upon.

For each of cohorts 1, 2, and 3, we will conduct separate phase II studies. For each cohort, the objective is to rule out an unacceptably low ORR (CR + PR) of 15% ( $p_0 = 0.15$ ) in favor of an improved ORR (CR + PR) of 35% ( $p_1 = 0.35$ ). Using a Simon two-stage minimax design, assuming a power of 80% and a type 1 error rate (one-sided) of 10%, the first stage will enroll 10 participants. If during the first stage, 0 or 1 of the first 10 participants have a response, the cohort will stop early for futility. If 2 or more of the first 10 participants have a response, 12 additional participants will be enrolled in the cohort, for a total of 22 participants in that cohort.

In order to ensure that enrollment to the second stage is warranted, a temporary pause may be employed after accrual to the first stage if additional follow-up time is needed to assess the number of responses. If after the second stage, there are 6 or more participants with a response out of 22 ( $6/22 = 27.3\%$ ) participants, the treatment would be deemed interesting for further study in later trials. If 2 to 5 out of 22 participants have a response, then further investigation of the treatment would not be warranted.

The trial may accrue up to  $22 + 22 + 22 = 66$  evaluable participants if all three cohorts proceed to the second stage. To allow for a small number of inevaluable participants (9) and screen failures (20), the accrual ceiling will be set at 95. It is anticipated that up to 2-3 participants per month may be enrolled on this trial. Accrual is therefore expected to be completed within 3 years.

## 10.4 POPULATION FOR ANALYSIS

### 10.4.1 Evaluable for toxicity

Any participant receiving at least one dose of either agent will be evaluable for toxicity.

### 10.4.2 Evaluable for objective response

Only those participants who have measurable disease present at baseline, have received at least one cycle of therapy, and have had their disease re-evaluated at the restaging scans will be

considered evaluable for response. These participants will have their response classified according to the definitions stated in Section [6.3](#). (Note: Participants who exhibit objective disease progression before their scheduled first restaging scans may be considered evaluable).

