### Design:

- This is an open label, non-randomized Phase II pilot study with one Arm.
- SG will be administered intravenously (IV) at 10 mg/kg on Days 1 and 8 each 21-day cycle.
- Tumor assessments will be time-based: every 9 weeks ( $\pm$  1 week) for the first year and every 12 weeks ( $\pm$  1 week) thereafter until disease progression. Pre-treatment biopsies and serial blood samples will be collected for the correlative studies.
- Treatment will be given for a maximum of 5 years or until disease progression or unacceptable toxicities.
- Up to 66 evaluable participants will be enrolled.

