#### For Participants with Measurable Disease (i.e., Target Disease)

Target Lesions	Non-Target Lesions	New Lesions	Overall Response	Best Overall Response when Confirmation is Required*
CR	CR	No	CR	≥ 4 wks. Confirmation**
CR	Non-CR/Non-PD	No	PR	
CR	Not evaluated	No	PR	≥ 4 wks. Confirmation**
PR	Non-CR/Non-PD/not evaluated	No	PR	
SD	Non-CR/Non-PD/not evaluated	No	SD	Documented at least once ≥ 4 wks. from baseline**
PD	Any	Yes or No	PD	
Any	PD***	Yes or No	PD	no prior SD, PR or CR
Any	Any	Yes	PD	

Target Lesions	Non-Target Lesions	New Lesions	Overall Response	Best Overall Response when Confirmation is Required*
*				See RECIST 1.1 manuscript for further details on what is evidence of a new lesion.
**				Only for non-randomized trials with response as primary endpoint.
***				In exceptional circumstances, unequivocal progression in non-target lesions may be accepted as disease progression.
Note:				Participants with a global deterioration of health status requiring discontinuation of treatment without objective evidence of disease progression at that time should be reported as "symptomatic deterioration." Every effort should be made to document the objective progression even after discontinuation of treatment.

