## 10 STATISTICAL CONSIDERATIONS

### 10.1 OBJECTIVES AND ENDPOINTS

OBJECTIVES	ENDPOINTS	JUSTIFICATION FOR ENDPOINTS
Primary		
To determine the ORR of SG in participants with recurrent gynecological malignancies, calculated for each individual tumor histology by RECIST v1.1	ORR (RECIST v1.1) assessed by radiographical evaluation i.e., CT/MRI every 9 weeks (+/- 1 week) for the first year and then every 12 weeks (+/- 1 week) until PD or up to 5 years and at EOT which occurs within 14 days after the end of therapy.	Standard endpoint for phase 2 cancer clinical trials. Success of regimens will be determined by these endpoints.
Secondary		
To determine the safety of SG	Identify adverse events (AE) per CTCAE v5.0, by type and grade of toxicity on Days 1, 8, and 15 of each cycle, at EOT which occurs within 14 days after the end of therapy, and 30 days after the end of treatment. Beyond 30 days after the last intervention, only adverse events which are serious and related to the study intervention will be assessed.	Safety is a standard endpoint for clinical trials (collecting information on all major organ function and observed toxicity, if any, to determine prominent toxicity to advise safety).
To determine the PFS of participants receiving SG	Participants will be assessed for PFS by CT CAP at every restaging every 9 weeks for the first year and then every 12 weeks until PD or up to 5 years and at EOT which occurs within 14 days after the end of therapy.	Standard endpoints for correlative studies. These endpoints will explore changes within timepoints as stipulated within the protocol to understand the effect of SG.
To determine the OS of participants receiving SG	Participants will be assessed for OS from start of treatment. OS will be collected on Days 1, 8, and 15 of each cycle for up to 5 years, at EOT which occurs within 14 days after the end of therapy, 30-day safety visit and every 6 months during follow up for up to 10 years.	

OBJECTIVES	ENDPOINTS	JUSTIFICATION FOR ENDPOINTS
To determine the median DoR of SG	Participants will be followed until progression after completion of study therapy and assessed by CT CAP very 9 weeks for the first year and then every 12 weeks until PD or up to 5 years and at EOT which occurs within 14 days after the end of therapy.	
Exploratory		

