### **10.5.6 Planned Interim Analyses**

Interim analyses for efficacy will be performed after the first stage of the two-stage design as appropriate.

Separately for each cohort, after the first restaging scan of the last evaluable participant required for the interim analysis, enrollment to the cohort will be halted to allow for an analysis by the study team. An interim analysis report will be created to document the number of responses in the first stage. The memo will be provided to study sponsor prior to continuation of accrual. Alternatively, if the required number of responses is observed before that time, the memo may be generated, reviewed, and provided to the study sponsor at that point without a pause in accrual.

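### The response-evaluable rule in 10.4.2 removes treated participants, mostly likely non-responders, from the ORR and the Simon counts, so the ORR can be inflated and the false-positive rate can exceed 10%

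*Combined protocol and SAP*

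**What the plan says.** Section 10.4.2 is the only response population in the plan. Besides measurable disease at baseline, participants must "have received at least one cycle of therapy, and have had their disease re-evaluated at the restaging scans". A note adds one exception: "Participants who exhibit objective disease progression before their scheduled first restaging scans may be considered evaluable". Section 10.5.2 gives the ORR with a Clopper-Pearson interval for each cohort and names no other denominator.

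The trial is sized and monitored on the same basis. The Précis states "Up to 66 evaluable participants will be enrolled". Section 10.3 sets the ceiling: "To allow for a small number of inevaluable participants (9) and screen failures (20), the accrual ceiling will be set at 95". Section 10.5.6 places the stage 1 look "after the first restaging scan of the last evaluable participant required for the interim analysis". The plan never says outright that inevaluable participants are replaced, but 66 evaluable plus 9 inevaluable plus 20 screen failures makes 95, which implies it.

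Three other passages bear on the point. Section 10.1 schedules imaging "until PD or up to 5 years and at EOT which occurs within 14 days after the end of therapy". The note under the best-response table in 6.3.3.3 recognises symptomatic deterioration without objective progression, and adds: "Every effort should be made to document the objective progression even after discontinuation of treatment". For toxicity, 10.4.1 uses an any-dose rule: "Any participant receiving at least one dose of either agent will be evaluable for toxicity".

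**The concern.** First restaging is at about week 9 (3.1). A participant who dies, withdraws or declines clinically before any post-baseline scan, or who does not complete a cycle, drops out of both numerator and denominator. Such participants are very unlikely to have responded, so membership of the primary analysis set depends partly on the outcome of treatment.

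The exception does not close the gap. It covers objective progression only, and it is permissive. The decision to count someone is made in an open-label trial with the result already known, and one participant can decide a boundary of 2 in 10 or 6 in 22.

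At stake in each of the three cohorts are the reported ORR, the stage 1 futility decision and the final decision on further study. No all-treated ORR is planned against which a reader could judge the effect.

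**Working it through.** **Inputs.** From 10.3, per cohort: null rate 15%, target rate 35%, one-sided type I error 10%, power 80%; stop with 0 or 1 responses in 10; otherwise add 12; success at 6 or more of 22; 9 inevaluable places on top of 66 evaluable.

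**Formula.** For a response probability p among those counted,

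P(success) = Σ over x = 2 to 10 of P[Bin(10, p) = x] × P[Bin(12, p) ≥ 6 − x].

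**The plan's own figures.** At p = 0.15, P(success) = 0.0907. At p = 0.35 it is 0.8040. An exhaustive search over two-stage designs returns 1/10 and 5/22 as the minimax design. Section 10.3 is reproduced, and the true type I error of the design is 9.1%, which leaves little room below 10%.

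**Effect of the exclusions.** Let d be the fraction of treated participants who are excluded. Assume that all of them are non-responders, that they are replaced until 22 are evaluable, and that the true all-treated rate is 15%. The rate among those counted is then 0.15/(1 − d).

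| Case | d | Rate among evaluable | P(success) |
|---|---|---|---|
| None excluded | 0 | 15.0% | 9.1% |
| Crossing point | 2.5% | 15.4% | 10.0% |
| 2 of the 9 places are treated participants | 2/68 = 2.9% | 15.5% | 10.2% |
| One per cohort | 3/69 = 4.3% | 15.7% | 10.7% |
| Illustrative | 5% | 15.8% | 11.0% |
| Illustrative | 10% | 16.7% | 13.4% |
| All 9 places are treated participants | 9/75 = 12% | 17.0% | 14.5% |

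**Effect on the estimate.** A result on the boundary, 6/22 = 27.3%, becomes 6/23 = 26.1% of treated participants with one exclusion and 6/25 = 24.0% with three.

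**Sensitivity to the benchmark.** If 15% is itself a rate among evaluable participants, P(success) stays at 9.1% whatever d is. If the true all-treated rate is 10%, it is 0.10/0.88 = 11.4% among evaluable participants at d = 12%, and P(success) is 2.9%.

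**Power if all treated participants are counted.** If 35% is an all-treated rate, power is 80.4% as designed. If 35% was meant for evaluable participants only, the all-treated rate is 0.35 × (1 − d):

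| d | All-treated rate | Power with 10/22 |
|---|---|---|
| 5% | 33.3% | 75.6% |
| 10% | 31.5% | 70.2% |
| 12% | 30.8% | 67.8% |

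Repeating the minimax search at these lower rates (type I error at most 10%, power at least 80%) gives, at 5%, a first stage of 16 needing 3 or more responses and a total of 26 needing 7 or more (type I error 8.0%, power 80.2%). At 12% it gives a first stage of 21 needing 4 or more and a total of 32 needing 8 or more (9.1%, 80.2%).

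**The case against.** The strongest objection is that the type I error claim depends on a fact the plan does not supply. Section 10.3 takes its benchmark from published single-agent response rates of 10-15% and gives no denominator. If those are evaluable-only rates, the error rate is not inflated. Also, 15% is the top of that range: at the midpoint of 12.5%, the same calculation gives 4.4% with no exclusions and 7.3% with 12% excluded. This stands, and the error-rate figures hold only under the stated condition.

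Second, the realistic loss may be small. One excluded treated participant in the whole trial (1/67) gives 9.6%, still under 10%. Some of the 9 places may go to people who are enrolled but never dosed. Restaging is time-based until progression, and there is an end-of-treatment scan, so many who stop early will still be imaged. This also stands in part: 12% is an upper case. But 10.4.2 does not say whether the end-of-treatment scan counts as a restaging scan. No imaging schedule recovers those who die or withdraw unscanned, or who receive less than one cycle.

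Third, counting the unassessed as failures has a price if 35% is an evaluable-only rate. Power falls as shown above, and at the target the chance of wrongly stopping at stage 1 rises from 8.6% to 12.7% with 10% inevaluable. This is fair, and is why the basis of both rates must be stated.

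Finally, this is a pilot whose positive result leads only to further study. That limits the consequence. It does not justify a primary denominator that depends on outcome, or a discretionary rule for early progressors.

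**Conclusion.** The concern holds and should be fixed. As written, entry to the primary ORR and to both Simon stages depends partly on what happens after treatment starts, and the ORR can be biased upward in every cohort. That conclusion does not depend on the benchmark.

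The effect on the error rate is modest and conditional. If 15% is an all-treated rate and those excluded are non-responders, the false-positive rate passes 10% once about 2.5% of treated participants are excluded, is 10.7% at one per cohort, and reaches 14.5% if all 9 allowance places are treated participants. If 15% is an evaluable-only rate, it stays at 9.1%. The documents give neither the benchmark's denominator nor an expected rate of early loss.

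**What to change.** - In 10.3, 10.4.2, 10.5.2 and 10.5.6, base the primary ORR and both stage counts on all participants with measurable disease at baseline who receive at least one dose of SG. This matches the any-dose principle in 10.4.1.
- Count participants with no post-baseline assessment as non-responders, and do not replace them.
- Replace the permissive note in 10.4.2 with a fixed rule: participants with objective progression before the first restaging scan are evaluable and are counted as non-responders.
- Keep the present evaluable set as a sensitivity analysis, and state whether the end-of-treatment scan counts as a restaging scan for it.
- State in 10.3 whether 15% and 35% are all-treated or evaluable-only rates. If evaluable-only, restate the power.

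**Cost.** If both are all-treated rates, the change is wording only: n and boundaries stay, type I error is 9.1% and power 80.4%, up to 9 fewer participants are treated, and the reported ORR is slightly lower. If 35% is an evaluable-only rate, power falls to 75.6%, 70.2% or 67.8% at 5%, 10% or 12% inevaluable. Restoring 80% would take 26 per cohort at 5% (3 × 26 = 78, against 66 + 9 = 75 now budgeted) or 32 at 12% (3 × 32 = 96, above the ceiling of 95 before any screen failures). The alternative is to state the lower power and accept it for a pilot.

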## **10.5 STATISTICAL ANALYSES**

### **10.5.1 General approach**

ORR will be reported by disease cohort along with a confidence interval.

Toxicities will be reported by grade and type; PFS, and OS will be reported by cohort along with a confidence interval.

### **10.5.2 Analysis of the Primary Endpoint**

ORR (the fraction of PR or CR) will be calculated along with a 95% confidence interval for each cohort.

The proportion of participants who achieve a response will be reported separately for each cohort, along with 95% confidence intervals (Clopper-Pearson).

### **10.5.3 Analysis of the Secondary Endpoints**

#### **10.5.3.1 Safety**

Safety will be reported by describing AE per CTCAE v5.0, by type and grade of toxicity, as detailed in Section [6.3](#).

#### **10.5.3.2 Clinical Efficacy**

The assessment of clinical activity as determined by:

- DOR will be calculated by the Kaplan-Meier method, starting at date response was identified until progression or the response is declared to have ended, if the participants have a PR or CR. The median DOR will be reported along with a 95% confidence interval by cohort.
- PFS will be calculated from on-study date until date of progression or death without progression, using the Kaplan-Meier method by cohort. The median PFS will be reported along with a 95% confidence interval by cohort.
- OS will be calculated from on-study date until date of 10-year follow-up, using the Kaplan-Meier method by cohort. The ten-year OS rate, which is the percentage of people in a study or treatment group who are alive ten years after their initiation of the study treatment. The median OS will be reported along with a 95% confidence interval by cohort.

#### **10.5.4 Safety Analyses**

To assess safety in previously treated ovarian, endometrial, and cervical cancer participants, the toxicity grade and type will be reported for all participants treated in the three cohorts or separately by cohort.

#### **10.5.5 Baseline Descriptive Statistics**

Baseline demographic characteristics will be reported, separately by disease cohort.

### **10.5.6 Planned Interim Analyses**

Interim analyses for efficacy will be performed after the first stage of the two-stage design as appropriate.

Separately for each cohort, after the first restaging scan of the last evaluable participant required for the interim analysis, enrollment to the cohort will be halted to allow for an analysis by the study team. An interim analysis report will be created to document the number of responses in the first stage. The memo will be provided to study sponsor prior to continuation of accrual. Alternatively, if the required number of responses is observed before that time, the memo may be generated, reviewed, and provided to the study sponsor at that point without a pause in accrual.

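### Sections 10.3 and 10.5.6 disagree on when accrual stops for the stage-1 futility look and on whether stopping is mandatory, so stage-2 participants can be enrolled before the look is made

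*Combined protocol and SAP*

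**What the plan says.** Section 10.3 sets the same design for each cohort. The aim is "to rule out an unacceptably low ORR (CR + PR) of 15" per cent "in favor of an improved ORR (CR + PR) of 35" per cent. The error rates and first stage are given as "assuming a power of 80% and a type 1 error rate (one-sided) of 10%, the first stage will enroll 10 participants". If "0 or 1 of the first 10 participants have a response, the cohort will stop early for futility". With 2 or more responses, "12 additional participants will be enrolled in the cohort, for a total of 22 participants in that cohort". Six or more responses in 22 count as success.

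On stopping accrual for the look, Section 10.3 says that "a temporary pause may be employed after accrual to the first stage if additional follow-up time is needed" to count responses. Section 10.5.6 says that "after the first restaging scan of the last evaluable participant required for the interim analysis, enrollment to the cohort will be halted" so that the study team can do the analysis. It requires a memo to the sponsor before accrual continues, and it waives the pause if the required number of responses has already been seen.

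Three other provisions matter. Restaging is every 9 weeks, plus or minus 1 week, in the first year (Section 3.1). Evaluability for response generally needs one cycle and a restaging scan, though early progression may also count (Section 10.4.2). On accrual, "It is anticipated that up to 2-3 participants per month may be enrolled on this trial" (Section 10.3).

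**The concern.** The two sections differ in two ways. On timing, Section 10.3 puts the pause at the end of stage-1 accrual, and Section 10.5.6 puts the halt about 9 weeks later. On force, the first is optional and the second is mandatory. The mandatory stop therefore comes after the period in which the futility answer is pending, and the only stop that covers that period is discretionary.

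The stage-1 rule exists so that 12 more people are not treated in a cohort where the drug looks inactive. The waiver in Section 10.5.6 gives no protection here, because a cohort that stops for futility has by definition not reached 2 responses. The open window is thus sure to fall in the cohorts that fail. The plan also does not say how participants enrolled beyond the first ten are handled if the cohort is then declared futile. At a true rate of 15%, two such participants would yield at least one response with probability 1 − 0.85² = 28%, so a cohort stopped at 1/10 could later show responses for which no rule exists.

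**Working it through.** **Inputs.** From Section 10.3: null rate 0.15, target rate 0.35, stop at 0 or 1 of 10, success at 6 or more of 22, accrual of 2 to 3 per month for the whole trial. From Section 3.1: first restaging at 9 weeks (8 to 10). The split of accrual over the three cohorts is not stated. I assume equal thirds and take all accrual in one cohort as the upper bound. One month is 365.25/12/7 = 4.348 weeks.

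**The plan's own design.** The probability of declaring success is the sum over x = 2 to 10 of P(X₁ = x) × P(X₂ ≥ 6 − x), with X₁ ~ Bin(10, p) and X₂ ~ Bin(12, p). It is 0.0907 at p = 0.15 and 0.8040 at p = 0.35, within the stated 10% and 80%. An exhaustive search returns 1/10 and 5/22 as the minimax design, so the stated figures reproduce.

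**Chance of a futility stop.**
- At 15%: 0.85¹⁰ + 10 × 0.15 × 0.85⁹ = 0.1969 + 0.3474 = 0.544.
- At 35%: 0.086.

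**Expected size at 15% with no overrun.** 10 + 12 × (1 − 0.544) = 15.5.

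**Overrun if Section 10.5.6 is followed, the Section 10.3 pause is not used and fewer than 2 responses have been seen.** The overrun k is the cohort's monthly rate × 9 / 4.348. Extra participants add to the total only when the cohort stops; otherwise they take stage-2 places. Expected size is therefore 15.47 + 0.544 × k.

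| Accrual to the cohort | Overrun k in 9 weeks | Expected size at 15% |
|---|---|---|
| Equal split, 2/month overall | 1.38 | 16.2 |
| Equal split, 3/month overall | 2.07 | 16.6 |
| All in one cohort, 2/month | 4.14 | 17.7 |
| All in one cohort, 3/month | 6.21 | 18.8 |

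Over the 8-to-10-week window the equal-split overrun runs from 1.2 to 2.3.

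**If the accrual rate includes screen failures.** The ceiling of 95 comprises 66 evaluable, 9 inevaluable and 20 screen failures, and 95 over 36 months is 2.6 per month, which fits the quoted rate. On that inference the treated share is 75/95, and the equal-split overrun falls to 1.38 × 75/95 = 1.1 up to 2.07 × 75/95 = 1.6. Expected size is then 16.1 to 16.4.

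**Exposure before the scan.** Nine weeks is the maximum, for someone who starts immediately after the tenth participant. With even accrual the average is about 9/2 = 4.5 weeks.

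**Error rates.** If the first ten evaluable participants alone decide stage 1, the calculation of 0.0907 and 0.8040 is untouched by when accrual pauses.

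**The case against.** The strongest reply is that the two sections can be read in sequence. Section 10.3 pauses for follow-up and Section 10.5.6 halts for analysis and the sponsor memo; these are different purposes. Section 10.3 also makes the 12 further participants conditional on 2 responses, so a careful team would use the pause. The overrun is small on any likely split, and how much accrual to allow during follow-up is a legitimate trade-off between overrun and delay.

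Much of this stands. A reader might infer that the plan commits stage-2 participants to about 9 weeks of treatment before the futility decision. The documents do not support that: the Section 10.3 pause makes overrun permitted, not inevitable; 9 weeks is the longest exposure; and only those enrolled in the window are affected. A reader might also infer that the test is compromised. It is not, because the rule rests on the first 10.

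The sequential reading does not remove the problem. The earlier pause remains optional, so a team that skips it complies with both sections while breaking the condition that Section 10.3 itself sets for opening stage 2.

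**Conclusion.** The point holds as an inconsistency that should be resolved. The realistic size is about 1 to 2 extra participants per cohort, assuming equal accrual across cohorts at the stated rate and no use of the optional pause. The figure of about 4 to 6 needs all of the trial's accrual to fall in one cohort, which nothing in the documents suggests. At a 15% response rate the chance that the cohort then stops is 54%, and expected size rises from 15.5 to about 16 to 16.6. Type I error and power are unchanged. The matter is one of participant protection and a clear rule, not of inference.

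**What to change.** In Section 10.5.6, state that:
- enrollment to a cohort halts once ten participants have started treatment;
- it reopens before the look only to replace a participant found inevaluable;
- it resumes to stage 2 only when the memo documents at least 2 responses;
- no pause is needed if 2 responses are already documented.

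The trigger should be ten participants started, not ten evaluable participants started, because under Section 10.4.2 nobody is known to be evaluable at treatment start. Make the pause in Section 10.3 mandatory on the same terms. State that anyone enrolled beyond the stage-1 ten counts toward stage 2 only.

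The text change is a few sentences. The operational cost is a pause of about 9 weeks, only in a cohort that has not yet shown 2 responses. It is longer if an inevaluable participant must be replaced. It is also longer if the look counts only confirmed responses: Section 6.3 puts the confirmatory scan 4 to 8 weeks after first documentation, so a response first seen at that scan would take the wait to 13 to 17 weeks. Section 10.5.6 does not say whether confirmation is needed at the look, and should.
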